13.0 CRITERIA FOR REMOVAL FROM STUDY

Participants will be removed from study when any of the criteria listed in Section 13.1 applies. All reasons for discontinuation of therapy should be documented clearly in the medical record. The patient should be followed-up per protocol.

13.1 Discontinuation of Treatment

Reason for discontinuation from study will be documented in the Case Report Form, and may include:

- Non-compliance with the study protocol, including not attending the majority of scheduled visits
- Unacceptable major toxicity
- Intercurrent illness or condition that would in the judgment of the treating investigator, significantly affect assessment of clinical status or require discontinuation of study treatment
- Subject's request
- Study closure

13.2 Study Withdrawal

Reasons for withdrawal from study include:

- Subject withdrawal of consent
- Subject lost to follow up
- Study termination

14.0 BIOSTATISTICS

The primary endpoint of the study is defining the MTD of rucaparib in combination with RT to the breast/ chest wall with or without regional nodes.

The trial will be monitored using TITE-CRM. Assuming a model for the time to occurrence of toxic response as a function of dose, the method allows information from all enrolled patients to be used when allocating a new patient to a dose level. Subjects can be continuously recruited throughout the trial, as long as patients are treated at a dose consistent with the current safety profile.

The definition of dose-limiting toxicity (DLT) for this trial is defined in Section 9.5 above.

The acute observation period for toxicity is defined as 10 weeks, which includes the 6-week rucaparib and radiotherapy treatment course and a 4-week post RT rucaparib maintenance period.

The target rate for dose-limiting toxicity is 30%. This level was selected upon rates of toxicity observed in a recent phase I study of veliparib + chest wall RT in breast cancer patients [14]. The target rate will define the maximum tolerated dose (MTD) of rucaparib given concurrently with radiotherapy for residual invasive disease after neoadjuvant chemotherapy.

The expected rates of acute toxicity have been estimated based upon previous treatment experience with radiotherapy for these indications, and clinically acceptable maximal levels of toxicity. These rates will be re-estimated throughout the conduct of this trial as treatment experience is accrued.

Dose allocation

Phase I dose levels corresponding to expected toxicity rates are presented in the following table. Rucaparib will be escalated in this protocol as shown below, concurrently with a standard radiotherapy treatment plan, delivered in 2 Gy fractions, 5 days a week, over 5-6 weeks, delivered to the breast or chest wall with or without regional nodal basins.

Intrasubject escalation of the rucaparib dose is NOT allowed.

Regimen level	Expected probability of toxicity
-1 (300 mg BID)	10%
0 (400 mg BID)	17%
1 (500 mg BID)	24%
2 (600 mg BID)	30%

Doses will be allocated to patients according to the TITE-CRM criterion, as summarized here. Start of the CRM algorithm is dose level 0.

As of 8/7/2019, we have accrued 7 out of 30 patients to this trial. Two patients were accrued to dose level 0 (400 mg BID) and 5 to dose level -1 (300 mg BID). Based on the data, dose level -1 has been found to exceed our targeted 30% DLT rate. We have therefore added three additional lower dose levels, one at 200 mg BID (dose level -2), another at 300 mg QD (dose level -3) and a third at 200 mg QD (dose level -4). The revised dose allocation table and revised expected probability of toxicity is provided in the table below. The expected probability of toxicity takes into account accrued data up to 8/7/2019. All the patients will be is determined by the TITE-CRM based on all patient toxicities.

Regimen level	Expected probability of toxicity
-4 (200 mg QD)	20%
-3 (300 mg QD)	30%

-2 (200 mg BID)	40%
-1 (300 mg BID)	50%
0 (400 mg BID)	62%
1 (500 mg BID)	70%
2 (600 mg BID)	76%

- When a patient presents for enrollment on this trial, the probability of toxicity will be estimated for each dose level, based upon the initial expectations of toxicity and the incidence of toxicity in patients already treated, weighted by the amount of time those patients have been followed during the acute observation period. The level that has estimated toxicity closest to the target rate subject to conditions below, will be selected.
- In the extremely rare event a patient is removed from study prior to completing the acute observation period, for reasons unrelated to toxicity, the patient will be considered not to have experienced a DLT event. The patient will contribute her weighted follow-up experience to the estimate of the probability of toxicity up until the date of discontinuation. Her information will not be used following the date of discontinuation.
- The dose level cannot be escalated until at least two patients have been observed for the entire acute toxicity period (70 days). This rule will be followed throughout the trial.
- Dose escalation is restricted to one level between adjacent patients.
- There is no restriction on the number of levels that the dose may be reduced between patients.
- A maximum of 4 patients per calendar month can be enrolled.
- Patients 1 and 2 will be assigned to dose level 0.
- For patients 3 to 15, the dose level estimated to have probability of DLT closest to but not exceeding the target rate, 30%, by more than 5% (i.e. 35% predicted probability) will be assigned to the newly enrolled patients.
- For patients 16 to 30, the dose level with probability of DLT closest to, but not exceeding the target rate, 30%, will be assigned the newly enrolled patient.

Under this allocation schema, the dose level of rucaparib will increase until toxicity is observed, and then will tend to vary around the level producing the target rate of toxicity. In order to allocate treatments, the protocol statistician must be notified promptly of all dose-limiting toxicities.

The TITE-CRM algorithm selects the MTD as the dose level yielding a toxicity rate closest to the target toxicity level from either above or below. In our last two rules above, we will override the TITE-CRM algorithm so that dose assignments will be made closest to the target toxicity level, not exceeding it by 5% for the first 15 patients and not exceeding it for patients 16 to 30. This is a conservative approach. Thus, the true conduct of the trial will have lower

expected toxicity rates than indicated in the operating characteristics shown below. Allowing 5% above the target toxicity for the first 15 patients is still more conservative than the TITE-CRM without the override rules we have written in. The rule is different for the first 15 patients to allow for a slightly faster dose escalation.

Regimen level	Rucaparib dose	Prior estimates	Scenario 1	Scenario 2	Scenario 3	Scenario 4
-1	300 mg BID	10%	10%	10%	17%	24%
0	400 mg BID	20%	17%	17%	24%	30%
1	500 mg BID	30%	24%	30%	30%	40%
2	600 mg BID	40%	30%	40%	40%	50%

Operating Characteristics

As listed in table 1 below, we will examine 6 dose levels and it is our prior expectations that dose level 2 is the MTD. Our initial estimates of DLT probabilities are: 0.10, 0.20, 0.30, and 0.40 for doses -1-2, respectively. The operating characteristics of this trial design were evaluated using repeated simulations of possible trial conditions, both near to and far from expectation for toxicity. Four trial scenarios are presented in the table below. First, the true probability of toxicity at each dose level is as expected. Second and third, the true probability of toxicity at each dose level is mildly higher than expected. Fourth, the true probability of toxicity at each dose level is moderately higher than expected. The dose level at our target toxicity is in gray. The trial begins at dose level 0.

Table 1: Hypothetical Scenarios

Through 1000 simulated trials with the above parameters, we expect the method to behave in the following way, assuming the 4 hypothetical scenarios described in the table above.

All simulations were run and summarized using the R package *dfcrm*. It is assumed that patients will be accrued according to a Poisson arrival process, at a rate of 4 per every 70 days.

Table 2: Percent of simulated trials that selected each dose under each scenario

Dose levels	-1	0	1	2
Scenario 1	.4%	9.7%	26.5%	63.4%
Scenario 2	1.0%	20.5%	49.4%	29.1%
Scenario 3	7.7%	26.8%	40.7%	24.8%
Scenario 4	30.2%	43.2%	22.7%	3.9%

Table 3: Expected number of patients treated at each dose under each scenario

Dose levels	-1	0	1	2
Scenario 1	1.576	4.645	7.546	16.233
Scenario 2	2.342	6.932	10.053	10.673
Scenario 3	4.428	7.972	8.502	9.098
Scenario 4	9.239	9.586	6.787	4.388

Table 4: Average toxicities across trials at each dose

Dose levels	-1	0	1	2
Scenario 1	.139	.768	1.715	4.753
Scenario 2	.224	1.154	2.975	4.203
Scenario 3	.716	1.861	2.486	3.587
Scenario 4	2.136	2.866	2.683	2.190

Based on the above scenarios, the trial is estimated to take a median of 19-20 months to complete.

Amended Operating Characteristics

Due to the observed data, we have amended the trial to include three cohorts, -2, -3 and -4. The scenarios and simulations have now been adjusted as follows: (note tables are numbered Table 1a, Table 2a, Table3a, and Table 4a, where 'a' refers to amended scenarios and simulations. As of 8/7/2019, 7 patients are on trial. A total of 23 out of 30 patients remain to be accrued.

Table 1a: Hypothetical Scenarios

	Dose	Scenario 1	Scenario 2	Scenario 3	Scenario 4	Scenario 5	Scenario 6
-4	200 mg QD	1	1	1	10	20	30
-3	300 mg QD	4	5	5	20	30	40
-2	200 mg BID	6	10	10	30	40	45
-1	300 mg BID	12	20	20	40	45	50
0	400 mg BID	16	25	30	50	50	55
1	500 mg BID	20	30	40	60	55	60

2	600 mg BID	30	45	50	70	60	65
---	------------	----	----	----	----	----	----

Through 1000 simulated trials with the above parameters, we expect the method to behave in the following way, assuming the 6 hypothetical scenarios described in Table 1a above:

Table 2a: Rate a dose is selected under each scenario

	Scenario 1	Scenario 2	Scenario 3	Scenario 4	Scenario 5	Scenario 6
-4	0	0	0	0.025	0.22	0.556
-3	0	0	0.002	0.236	0.429	0.275
-2	0.007	0.017	0.033	0.419	0.226	0.113
-1	0.028	0.173	0.235	0.258	0.09	0.037
0	0.136	0.298	0.442	0.058	0.023	0.016
1	0.296	0.36	0.253	0.003	0.011	0.002
2	0.533	0.152	0.035	0.001	0.001	0.001

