12.0 CRITERIA FOR THERAPEUTIC RESPONSE/OUTCOME ASSESSMENT

The primary endpoint of the study is defining the MTD of rucaparib in combination with RT to the breast/chest wall with or without regional nodes.

The trial will be monitored using TITE-CRM, which is described in Section 14.0.

Sample Size

The study will enroll 30 patients who are able to complete the acute observation period without a dose-limiting event, or who experience a DLT for the estimation of the dose-toxicity function. We expect to accrue about 4 patients about every two months, therefore completing accrual in approximately 1-2 years.

Cohort Size

Subjects will be recruited as available and allocated to treatment according to the estimated toxicity rates. No formal cohort size is required; however, at least 2 patients must be observed for their entire acute toxicity period (70 days) before dose escalation is allowed. This rule will be followed throughout the trial.

Endpoint Definition

Locoregional relapse is defined as a recurrence of disease in the breast, chest wall, axilla, supraclavicular or internal mammary areas. Distant relapse is defined as a recurrence of breast cancer in any part of the body outside of the locoregional sites described above (ie bone, liver, brain).

Evaluability

Any subject receiving at least one dose of rucaparib and at least one fraction of RT will be considered evaluable for toxicity. Subjects who do not initiate treatment with either rucaparib or RT will be replaced and will not influence the TITE-CRM dose assignment algorithm. Any subject who discontinues trial therapy after receiving at least one dose of rucaparib and one radiotherapy fraction, but prior to completing the entire course of study treatment for reasons not due to toxicity, will also be replaced. These subjects will not count toward the sample size goal of 30 subjects; however, partial information from discontinuing subjects up until the date of discontinuation will be used by the TITE-CRM algorithm when making dose level assignments. Thus, these subjects' information will NOT be used following the date of discontinuation for future dose assignments. At the trial's conclusion, posterior estimates for the probability of toxicity at each dose level will be

made using only the 30 subjects with complete data (i.e. subjects that complete the acute observation period without a dose-limiting event, or those that experience a DLT).

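### The amended operating characteristics (Tables 2a–4a) do not start from the revised toxicity estimates and look like a fresh 23-patient trial that ignores the seven patients already treated

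*Combined protocol and SAP*

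**What the plan says.** Section 14.0 (Dose allocation) reports seven patients treated by 8/7/2019: "Two patients were accrued to dose level 0 (400 mg BID) and 5 to dose level -1 (300 mg BID"). It states that "dose level -1 has been found to exceed our targeted 30% DLT rate" and adds levels -2, -3 and -4. The revised estimates for levels -4 to 2 are 20, 30, 40, 50, 62, 70 and 76%, and "The expected probability of toxicity takes into account accrued data up to 8/7/2019". Later assignments are "determined by the TITE-CRM based on all patient toxicities".

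The allocation rule is "The level that has estimated toxicity closest to the target rate subject to conditions below, will be selected". For patients 3 to 15 this becomes the "dose level estimated to have probability of DLT closest to but not exceeding the target rate, 30%, by more than 5" percentage points, that is, no higher than 35%. Section 12.0 (Evaluability) says the final posterior estimates are "made using only the 30 subjects with complete data".

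The Amended Operating Characteristics say the scenarios and simulations were adjusted because of the observed data, with seven patients on trial and 23 to come. Tables 2a–4a follow, introduced with "Through 1000 simulated trials with the above parameters, we expect the method to behave in the following way, assuming the 6 hypothetical scenarios". The prior (skeleton), start level and prior variance of these runs are not stated, nor is the way the seven patients enter them. The later description of the TITE-CRM names a one-parameter logistic model.

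**The concern.** Tables 2a–4a are the amended design's only stated evidence that 23 more patients can locate the MTD, which is the primary objective. A reader will take them as the properties of this trial from 8/7/2019 onwards. Table 3a, however, has almost no one at level -3 in Scenarios 1–3, although the revised estimates place that level exactly on target. If the simulations leave out the seven patients, they describe a different trial from the one being run. Their most favourable rows (Scenarios 1 and 2, with the MTD at level 2 or 1) would then look more attainable than they are.

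**Working it through.** **1. Start level, without simulation.** The distance from the 30% target is |30 − 30| = 0 at level -3, |40 − 30| = 10 at -2 and |20 − 30| = 10 at -4. The rule picks -3 with or without the 35% cap, and dose reductions are unrestricted. Every Table 3a column sums to 23.0, so only new patients are counted. If the 8/7/2019 estimates govern the first simulated patient, the mean at -3 is at least 1.0 in every scenario. Table 3a gives 0.341, 0.611 and 0.774 in Scenarios 1–3.

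**2. What reproduces the tables.** A TITE-CRM was re-implemented in dfcrm style: linear weights over 70 days, Poisson accrual of 4 per 70 days, one-level escalation limit, prior variance 1.34 (assumed). One version was a fresh 23-patient trial with prior 10/20/30/40/50/60/70%, power model, start at -2, no caps and no earlier patients. Scenario 1 patients per level (2,000 trials):

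| Level | -4 | -3 | -2 | -1 | 0 | 1 | 2 |
|---|---|---|---|---|---|---|---|
| Fresh run | 0.17 | 0.30 | 2.92 | 3.15 | 4.13 | 5.19 | 7.14 |
| Table 3a | 0.21 | 0.34 | 2.91 | 2.93 | 3.68 | 4.96 | 7.97 |

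Over all 42 cells the root-mean-square gap is 0.25 patients (0.27 in repeat runs) and the largest gap is 0.83. Other choices fit less well:

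- fresh from -2, uncapped, all priors and models tried: 0.25–1.60;
- fresh with caps: 0.73–1.82;
- seven patients kept, two DLTs among them: 1.00–3.64;
- seven patients kept, three or four DLTs: 1.80–4.66.

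**3. The revised estimates already appear to contain the seven.** The original simulation prior for levels -1 to 2 was 10/20/30/40%. Raised to the power 0.30 it gives 0.501, 0.617, 0.697 and 0.760, which is the revised 50/62/70/76%. Reversing the exponent for the new levels gives 0.20^(1/0.30) = 0.5%, 0.30^(1/0.30) = 1.8% and 0.40^(1/0.30) = 4.7%. The implied prior is therefore 0.5/1.8/4.7/10/20/30/40%.

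Under that prior (power model, variance 1.34, full follow-up), 0/2 DLTs at level 0 and 4/5 at -1 give 50.1/61.7/69.7/76.0%. Three DLTs give 35–38% at -1 and two give 24–26%. Three at an average follow-up weight of 0.62–0.75, or two at 0.20–0.43, also give about 50%. The count is not identified, and using the published table as prior while adding the seven again would count them twice.

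**4. Seven patients entered once** (full follow-up assumed, caps on and off, power and logistic models). Scenario 1, level 2 selected, stated 53.3%:

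| DLTs among the seven | Implied prior | Five other priors |
|---|---|---|
| Four | 0% | 0–12% |
| Three | 0–6% | 0–37% |
| Two | 12–29% | 7–60% |

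Average patients at level 2 in Scenario 1, stated 7.97: at most 0.2 with four DLTs and 2.0 with three, under all six priors. Scenario 2, level 1 selected, stated 36.0%: 0–2% (four) and 4–12% (three) under the implied prior, 0–23% and 4–34% under the others. Scenarios 3–6, correct selection, implied prior, three or four DLTs: 22–51, 45–52, 40–52 and 31–66%, against the stated 44.2, 41.9, 42.9 and 55.6%.

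**5. The published table used as the prior, without re-adding the seven.** Starting at -3 with caps, Scenario 1 selects level 2 in 40–51%, near the stated figure, but places 1.9–2.7 patients at -3. Forcing the start to -2 (uncapped) gives 0.84 at -3 under the logistic model and 1.4–1.5 under the power model. None gives 0.341.

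**6. Plausibility of Scenarios 1 and 2.** They assume 12% and 20% DLTs at level -1. The binomial probability of at least 3/5 is 1.4% and 5.8%; of at least 4/5, 0.1% and 0.7%.

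**7. Table 4a, Scenario 6.** The column repeats Table 3a and sums to 23.0 DLTs in 23 patients. Table 1a rates times Table 3a counts give 0.30×10.166 + 0.40×4.642 + 0.45×4.643 + 0.50×2.085 + 0.55×0.876 + 0.60×0.418 + 0.65×0.170 = 8.9.

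**The case against.** The minimum of one patient at -3 holds only if the 8/7/2019 estimates govern the first simulated patient. The original simulations did not work that way: their prior put level 1 at 30%, yet they began at level 0. The estimates are also a snapshot, recalculated when each patient presents. Under the implied prior with full follow-up, three DLTs give 25–28% at -2 and 16–19% at -3, so the next patient would start at -2. Two DLTs would start at -1. A correct re-run could therefore average fewer than one patient at -3. The DLT counts are unseen, the implied prior is back-solved with a power model where the text says logistic, and the fresh run was chosen because it fits. The effect is confined to scenarios that the data make unlikely.

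Most of this stands as a limit on the claim. It does not reconcile the tables. The original start at level 0 was fixed in the conduct rules, whereas no fixed start is given for patient 8. The amended simulations are tied to the same date and the same 23 remaining patients as the estimates. The histories that start above -3 do not reproduce Table 3a either: no run with the seven kept came closer than 1.00 patients root-mean-square, against 0.25 for the fresh run. If a fixed start at -2 was intended, it had to be stated.

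**Conclusion.** The concern holds. Table 3a cannot come from simulations that begin at the revised estimates, and Tables 2a–4a behave like a fresh trial of 23. The first statement needs only the condition that those estimates apply to the first simulated patient. The second is a best-fit inference, because the simulation inputs are not stated.

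The size depends on DLT counts that the documents do not give. Under the implied prior, Scenario 1 selection of level 2 falls from 53.3% to between 0% and 29%. Across all priors tried the range is 0–60%, so with two DLTs and the flattest priors there is no overstatement. Scenario 2 is overstated for three or four DLTs; Scenarios 3–6 show no uniform bias. The Scenario 6 column of Table 4a is wrong whatever view is taken of the rest. The caps left out of the simulations are disclosed in Section 14.0 and form no part of this point. The defect lies in the stated operating characteristics: assignment follows the allocation rules, so no patient's dose changes.

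**What to change.** Re-run the amended simulations with the seven patients' actual levels, DLT status and follow-up entered exactly once, under the allocation rules of Section 14.0 (caps, one-level escalation limit, 70-day rule). State the skeleton, model, prior variance and start level, and whether the seven enter through the prior or the likelihood. Reconcile the simulated start level with the revised estimates. Replace Tables 2a–4a, including the Scenario 6 column of Table 4a.

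The cost is some statistician time and a set of replacement tables, with no change to conduct. The figures for Scenarios 1 and 2 will probably look less favourable.

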Under the CRM paradigm, the relationship between dose and toxicity is summarized by a single-parameter (α) logistic model that represents the assumed relationship prior to the collection of any patient data. Information about the relationship between dose and toxicity can be summarized using the distribution of the parameter, updated according to the current data. For instance, we can estimate the probability of toxicity at assigned doses and the subsequent target dose as a function of α based on the current data. The toxicity results will be summarized as follows.

The distribution of α updated according to the current data and the corresponding dose-toxicity model will be calculated. Predictive intervals concerning the toxicity parameter will be provided using this updated distribution of α .

The posterior distribution of toxicity, which display the probability a future patient will experience toxicity at a given dose based on the current data, will be calculated for each tested level. The dose level of rucaparib that produces the target rate of toxicity will be determined from this.

The proportion of subjects encountering toxicity at each dose level will be reported.

Analysis of Secondary Endpoints

Toxicity profiles will be tabulated and summarized. Locoregional relapse and distant relapse will be estimated using Kaplan-Meier methods.

Correlations between locoregional and distant relapse with HRD status (deficient vs proficient) and stromal TILs (present vs absent) will be evaluated using Kaplan-Meier estimates and a log-rank test. Patient satisfaction, quality of life, and cosmetic outcomes will be summarized descriptively and graphically. Note, for the cosmesis outcome based on the RTOG scale as provided in the appendix, excellent and good cosmesis will be grouped together, and fair and poor will be grouped together. The rate of fair/poor cosmesis will be calculated and described. All statistical analyses of secondary endpoints are considered to be exploratory in nature as the sample size is expected to be small in this phase I study. Analyses will be done over all 30 patients accrued to the study and by dose cohort.

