Recently, a Phase I trial of veliparib and post-mastectomy RT in breast cancer patients with locally recurrent or inflammatory breast cancer reported dose-limiting toxicities in 4/30 patients¹⁶. Four dose levels of veliparib were tested (50 to 200 mg BID) with concurrent RT to the chest wall and nodes (50 Gy). Severe acute toxicity did not exceed 30%, even at the highest tested dose of veliparib (200 mg BID). Using these findings, the planning of a phase II trial testing the efficacy of veliparib and RT in breast cancer patients is currently in development. These findings underscore the importance of additional studies assessing the safety of PARP inhibitors with RT.

In a recently published series of 233 women with clinical Stage II-III breast cancer who underwent neoadjuvant chemotherapy (NAC), mastectomy and post-mastectomy RT at MSKCC, the rate of pathologic complete response (pCR) in TNBC patients was only 23%¹⁷. Failure to achieve pCR resulted in a higher 5-year locoregional recurrence rate compared to patients with HER2+ and hormone receptor-positive breast cancer (26% vs. 7% and 4%, $p<0.001$). Moreover, others have demonstrated the residual disease after neoadjuvant chemotherapy in TNBC is associated with significantly worse progression-free and overall survival¹⁸. The single notable effort to escalate therapy in these patients was recently reported by Masuda et al¹⁹ in the *New England Journal of Medicine*. In this phase III randomized trial, patients with incomplete responses after neoadjuvant chemotherapy were randomized to consolidation capecitabine vs null. Overall survival was longer in the capecitabine group. Although the trial was for all comers, the greatest improvement was seen in TNBC cases (OS 79 vs 70% at 5 years). Taken together, these results demonstrate the need for additional treatment intensification in TNBC patients with residual disease after neoadjuvant chemotherapy. Recently, the Keynote-522 has altered the landscape of early TNBC, and is a seminal trial that randomized 1174 women receiving NAC for early TNBC to either chemotherapy alone or with pembrolizumab 200 mg/m² every 3 weeks (2:1) (Schmid NEJM). Among the first 602 patients randomized, the pathological complete response rate (primary endpoint) was higher in the pembro arm (64.8%) compared to placebo (51.2%). The co-primary endpoint of event-free survival was also better with pembro, 91.3% vs 85.3%. These effects appeared to independent of PDL-1 status.

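### Relapse is to be estimated by Kaplan-Meier with no rule for deaths without relapse; cumulative incidence would remove a possible small upward bias at almost no cost

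*Combined protocol and SAP*

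**What the plan says.** The analysis of secondary endpoints in Section 14.0 states: "Locoregional relapse and distant relapse will be estimated using Kaplan-Meier methods". The comparisons of relapse by HRD status and by stromal TILs "will be evaluated using Kaplan-Meier estimates and a log-rank test".

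Section 12.0 gives the two event definitions, and death is part of neither: "Locoregional relapse is defined as a recurrence of disease in the breast, chest wall, axilla, supraclavicular or internal mammary areas", and "Distant relapse is defined as a recurrence of breast cancer in any part of the body outside of the locoregional sites described above".

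Section 14.0 mentions deaths only among the safety tabulations. It does not say whether a death without relapse is censored, counted as an event or treated as a competing event, and it names no cumulative-incidence method.

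Three further statements set the scale:

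- Follow-up is two years (Sections 1.0 and 9.7, Table 10B).
- The secondary analyses are declared exploratory: "All statistical analyses of secondary endpoints are considered to be exploratory in nature as the sample size is expected to be small".
- They cover the whole trial and its parts: "Analyses will be done over all 30 patients accrued to the study and by dose cohort".

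**The concern.** A patient who dies without a locoregional relapse can no longer have one. If she is censored at death, Kaplan-Meier spreads her remaining probability over the patients still at risk, as though she might yet relapse. The resulting 1-KM answers a hypothetical question: how many would relapse if nobody died first. The cumulative incidence answers the question a reader of the trial report will have in mind: what proportion of treated patients relapse. The first is never below the second.

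Relapse assessment is a named secondary objective in Section 2.0, so these curves will be reported and read as relapse probabilities. What is at stake is the accuracy and clear meaning of those descriptive figures. The dose-finding result does not depend on them.

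**Working it through.** The plan gives no expected relapse rate, event count or precision for this analysis, so it has no figure to reproduce. The check asks how far the two estimators can differ in a trial like this one.

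**Inputs**

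- Five-year locoregional recurrence of 26% in triple-negative patients without a complete response. Section 3.1: "Failure to achieve pCR resulted in a higher 5-year locoregional recurrence rate". It is read here as a Kaplan-Meier figure; the plan does not say which kind it is.
- Five-year survival of 79% or 70% in the triple-negative patients of the adjuvant capecitabine trial. Section 3.1: "OS 79 vs 70% at 5 years". It comes from a different population and serves only to bound the death rate.
- Follow-up of two years and 30 patients.
- Assumptions: constant, independent hazards and, for the upper bound, every death occurring before any locoregional relapse.

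**Hazards per year**

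- Locoregional relapse: h1 = -ln(0.74)/5 = 0.060
- Death: h2 = -ln(0.70)/5 = 0.071, or -ln(0.79)/5 = 0.047

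**Formulas**

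- Kaplan-Meier with deaths censored: 1 - exp(-h1 t)
- Cumulative incidence: h1/(h1 + h2) × [1 - exp(-(h1 + h2) t)]

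**Locoregional relapse at t = 2 years**

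- 1-KM: 1 - exp(-0.1204) = 11.35%
- Cumulative incidence, 70% survival: 0.458 × 0.2313 = 10.59%. Gap 0.76 points, or 0.23 of 30 patients.
- Cumulative incidence, 79% survival: 0.561 × 0.1932 = 10.84%. Gap 0.51 points, or 0.15 of 30 patients.

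**Sampling error.** The binomial standard error at 11.35% with n = 30 is sqrt(0.1135 × 0.8865/30) = 5.8 points. The larger gap is 0.76/5.8 = 0.13 of one standard error.

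**Sensitivity**

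| Change to the upper bound | Two-year gap (points) |
|---|---|
| 70% survival, half of deaths competing | 0.39 |
| 70% survival, one tenth of deaths competing | 0.08 |
| 79% survival, half / one tenth competing | 0.26 / 0.05 |
| Five-year recurrence of 4% or 7% (the other subtypes in Section 3.1), all cases above | 0.01 to 0.19 |

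If the 26% were itself a cumulative incidence, solving the second formula for h1 at five years with 70% survival gives h1 = 0.073. The two-year figures become 13.6% and 12.7%, a gap of 0.9 points, which is still far below the standard error.

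**Distant relapse.** The documents give no rates for this endpoint. Assuming 20-50% distant relapse at five years and 0.5-2% per year death without it, the two-year gap is 0.04 to 0.46 points.

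**Spread over single trials.** In 20,000 simulated trials of 30 patients at the upper bound, the mean gap was 0.76 points and the 95th percentile 2.2 points. The two estimates were identical in 12.5% of trials. With half the deaths competing, the mean gap was 0.39 points and the estimates were identical in 28%.

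**Dose cohorts.** The gap in one small cohort can be larger. In five patients with one relapse-free death followed by one relapse, 1-KM is 1/4 = 25% and cumulative incidence is 4/5 × 1/4 = 20%. The standard error at 20% is then sqrt(0.2 × 0.8/5) = 18 points.

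**The case against.** The strongest reply is that this makes no practical difference. The plan nowhere says that deaths are censored, the secondary analyses are openly exploratory, and the largest plausible gap is about one eighth of a standard error. Even that figure is generous: overall survival includes deaths after relapse, and the 26% comes from a post-mastectomy triple-negative series, whereas this trial also enrols lumpectomy patients and hormone-receptor-positive patients. All of this stands, and it fixes the level of the point. It does not supply the missing rule. A relapse-free death needs some status in the data set, and with a recurrence-only event under plain Kaplan-Meier that status would normally be censored.

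A reader might infer several stronger things, which the documents do not support:

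- **That the reported figures will certainly be too high.** Censoring of deaths is an inference from silence. Even under it, the estimates differ only if a relapse-free death is followed by a relapse in another patient.
- **That death is a common competing event, with a five-year gap of about 4 points (26% against 22%).** Planned follow-up is two years, and no split of deaths before and after relapse is given.
- **That the bias differs between HRD or TIL groups.** The plan gives no survival by these groups for the trial population from which a difference could be computed.
- **That distant relapse also competes because locoregional follow-up stops there.** Sections 13.1 and 13.2 do not list relapse among the reasons for discontinuation or withdrawal, and Section 13.0 keeps patients who come off treatment in follow-up.
- **That the log-rank test is invalid.** With deaths censored it compares cause-specific hazards, which is a legitimate comparison.

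**Conclusion.** The point holds in a limited form. Section 14.0 applies Kaplan-Meier to endpoints that exclude death and leaves deaths without relapse undefined. Under the default of censoring them, 1-KM can overstate the probability of relapse and cannot understate it.

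The expected overstatement for locoregional relapse at two years is at most about 0.5-0.8 percentage points (11.3% against 10.6-10.8%). That bound rests on constant independent hazards, the borrowed background rates, the 26% read as a Kaplan-Meier figure, and every death counted as competing. It falls below 0.4 points if half the deaths or fewer precede relapse. For distant relapse it is probably smaller, but that rests on assumed rates alone.

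Sampling error with 30 patients is several times larger, no conclusion of the trial would turn on the difference, and the MTD objective is untouched. This is a cheap improvement and should be ranked as such.

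**What to change.** In the analysis of secondary endpoints in Section 14.0, replace the Kaplan-Meier sentence with one stating that locoregional relapse and distant relapse will each be reported as cumulative incidence (Aalen-Johansen), with death without that event as a competing event and with 95% confidence intervals. Use the same estimator for the curves by HRD and TIL status. Keep the exploratory log-rank test and label it a comparison of cause-specific hazards.

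The cost is about one sentence of SAP wording and a standard R function. There are no extra visits and no change to sample size or dose allocation. The reported estimates will be equal to, or slightly lower than, those from Kaplan-Meier.
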